### 2.3 Anticipated Benefits

All participants in this study will receive a mobile health application that may help them increase their exercise.

Exercise is recommended by the American Diabetes Association for people with T1D due to its physical and mental health benefits.

Protocol Number 2000035846

August 13, 2024 Version #7

The benefits to science and other people may include a better understanding of how to engage more people with T1D into exercise. There is a need to increase exercise among individuals with T1D.

The risks of our participants developing hypoglycemia, hyperglycemia, or exercise-related injuries during or after exercise in the context of the study are the same as those of them performing exercise under their normal conditions of daily living. The exercise routines in our instructional videos will target standard exercise recommendations by the American Diabetes Association for adults with T1D, which the association has determined have long-term health benefits that outweigh their risks. Furthermore, our participants will be supported in exercise safety by the measures outlined above (blood glucose monitoring review by Drs. [name], [name], [name], and routine clinical support) which further decreases the risk to benefit ratio.

The skin irritation risks associated with wearing commercially-manufactured biosensor devices including the CGM and Fitbit in the context of the study are also the same as those from wearing these devices under normal conditions of daily living. Wearing a CGM is recommended in the American Diabetes Association standard of care, and wearing a Fitbit device is a common and popular strategy to increase exercise. These benefits further decrease the risk to benefit ratio.

There are standard risks of research including confidentiality breach, and distress when completing study questionnaires and interviews. The principal investigator [name] has determined in consultation with his mentors Drs. [name] and [name] that these are outweighed by the benefits described in the first paragraph.

### Version #7

# 3 Study Purpose and Objectives

### 3.1 Purpose

### **PRIMARY**

To trial a mobile intervention that promotes safe exercise in middle-aged adults with type 1 diabetes mellitus (T1D) and evaluate its feasibility, acceptability, and mathematical robustness.

### **SECONDARY**

Determine real-time mechanisms underlying physical activity behavior and T1D-related barriers.

### 3.2 Hypothesis

### **PRIMARY**

*Hypothesis 1-1*: The mobile intervention will meet standards of feasibility.

Hypothesis 1-2: The mobile intervention will generate positive user feedback and suggested refinements.

Hypothesis 1-3-1: The data will verify that a prior-constructed machine-learning algorithm that predicted exercise adherence in a prior dataset will continue to do so with acceptable accuracy (receiver-operator characteristic AUC .80, or precision-recall AUC .80 if <20% of days are lapses).

Hypothesis 1-3-2: The data will verify that prior detected patterns in blood glucose safety hazards will continue to appear with expected frequency (≥1 of the above patterns occurring in ≥80% of person-weeks).

Hypothesis 1-3-3: The data will verify that small or greater (d≥0.1) changes in blood glucose resulting from exercise are detectable by a Bayesian model.

### **SECONDARY**

Hypothesis 2-1-1: Fear of hypoglycemia and blood glucose trends over the past 3 hours will predict momentary motivation states for physical activity (timepoints T1-T2).

Hypothesis 2-1-2: Fear of hypoglycemia and glycemic metrics over the past week will predict motivation states for physical activity over the past week (timepoints T0-T2).

Hypothesis 2-2-1: Motivation states for physical activity over the past week will predict physical activity behavior change and adherence over the 4-week intervention period (T0-T1).

Hypothesis 2-2-2: Motivation states for physical activity over the past 3 hours will predict physical activity maintenance, over the 2 weeks following the intervention (T1-T2).

Protocol Number 2000035846

August 13, 2024 Version #7

Hypothesis 2-3: We expect interview themes among the proposed T1D population will include perception of connection among glycemic variation, fear of hypoglycemia, motivation states for physical activity, and performance of physical activity.

### 3.3 Objectives

Primary Objective 1. Evaluate the intervention for feasibility

Primary Objective 2. Evaluate the intervention for acceptability (i.e., user satisfaction)

**Primary Objective 3.** Evaluate the mathematical robustness of the intervention data-driven tools.

**Secondary Objective 1.** Examine whether recognized T1D-related physical activity barriers (fear of hypoglycemia, glycemic variation) predict momentary and long-term variation in motivation states for physical activity.

**Secondary Objective 2.** Examine whether motivation states for physical activity predict momentary and long-term variation in physical activity behavior change, adherence, and maintenance resulting from a T1D motivational physical activity intervention.

**Secondary Objective 3.** Qualitatively identify determinants and sequalae of motivation states for physical activity among adults with T1D.

August 13, 2024 Version #7

[figure not shown]
# 4 Study Design

Single group completing familiarization (2 weeks), intervention (4 weeks) and follow-up (2 weeks).

The primary objectives are addressed by observation of feasibility and weekly satisfaction interviews.

The secondary objectives are addressed by longitudinal quantitative observations (surveys, wearable biosensors) during all phases and a descriptive qualitative interview at follow-up.

Figure 3. Study design flow chart.

August 13, 2024

Version #7

### 4.1 Study Duration

Subjects will each participate for 9 weeks. Totally data collection will be 16 months and data analysis 4 months, for a total study period of 20 months.

### 4.2 Outcome Variables/Endpoints

### 4.2.1 Primary Outcome Variables/Endpoints

### **PRIMARY AIMS**

Primary Objective 1. Evaluate the intervention for feasibility

**Outcome Variable 1-1-1.** Participant use metrics (i.e., % completion of diary, % wear-time of biosensors, frequency of video usage, % received of text messages).

**Primary Objective 2.** Evaluate the intervention for acceptability (i.e., user satisfaction)

**Outcome Variable 1-2-1.** System usability scale (10 Likert-style items assessing aspects such as ease of use and degree of technical support needed,  $\alpha$ =.91) augmented with Likert-style survey items specially designed for this intervention.

**Primary Objective 3.** Evaluate the mathematical robustness of the intervention by evaluating its predictive performance upon exercise behavior.

**Outcome Variable 1-3-1.** Prediction accuracy for exercise adherence (receiver-operator characteristic, precision-recall).

**Outcome Variable 1-3-2.** Frequency of expected patterns in blood glucose safety hazards around exercise.

Outcome Variable 1-3-3. Changes in blood glucose resulting from exercise.

### 4.2.2 Secondary and Exploratory Outcome Variables/Endpoints (if applicable)

**Secondary Objective 1.** Examine whether recognized T1D-related physical activity barriers (fear of hypoglycemia, glycemic variation) predict momentary and long-term variation in motivation states for physical activity.

Outcome Variable 2-1-1. Cravings for Rest and Volitional Energy Expenditure (CRAVE) survey of motivation states for physical activity

2-1-1-a. "right now" want for physical activity

2-1-1-b. "right now" aversion for physical activity

2-1-1-c. "past week" want for physical activity

2-1-1-d. "past week" aversion for physical activity

Protocol Number 2000035846

August 13, 2024

Version #7

**Secondary Objective 2.** Examine whether motivation states for physical activity predict momentary and long-term variation in physical activity behavior change, adherence, and maintenance resulting from a T1D motivational physical activity intervention.

Outcome Variable 2-2-1. Physical activity, total counts

Outcome Variable 2-2-2. Physical activity, minutes of moderate-to-vigorous

Outcome Variable 2-2-3. Sedentary behavior, minutes

**Secondary Objective 3.** Qualitatively identify determinants and sequalae of motivation states for physical activity among adults with T1D.

Outcome Variable 2-3-1. Interview themes.

August 13, 2024

Version #7

# 5 Study Participants

### 5.1 Study Population

Middle-aged adults with T1D and sedentary lifestyle.

### 5.2 Number of Participants

We will screen up to 57 participants to meet our goal of selecting 24 participants.

### 5.3 Eligibility Criteria

In order to be eligible for inclusion in the study, an individual must meet all of the following criteria:

- 30-65 years old inclusive
- Diagnosis with type 1 diabetes (T1D) or other insulin deficiency diabetes (latent autoimmune disease of adulthood, diabetes secondary to pancreatitis)
- Sedentary (<1.0 exercise sessions/wk as assessed by question #6 of Paffenbarger Physical Activity Questionnaire)
- Smartphone ownership
- English literacy
- Under regular care by a healthcare provider (defined as attending at least one appointment in the past year, plus access to verified 24hr phone number to reach the provider's team for insulin dose adjustments if assistance is needed)
- Home Broadband wireless Internet or cell phone network (≥25 mbps downloads, ≥3 mbps uploads on google Internet speed test). This is used in ~98% of US households.

•

Any individual who meets any of the following criteria will be excluded from participation in this study:

- Diabetic ketoacidosis not clearly related to pump site failure in past 6 months
- >1 episode of severe hypoglycemia (altered mental and/or physical status requiring assistance from another person for recovery) in past 6 months
- A1c ≥10.0%
- Resting blood pressure >160mmHg systolic or >100 mmHg diastolic
- Myocardial infarction or angina in past 12 months
- Uncontrolled arrhythmia (e.g., Afib with RVR, new onset Afib, ventricular tachycardia, escape rhythms)
- Congestive heart failure (stage 3 or 4)
- Exercise-induced asthma (not controlled on inhalers)

August 13, 2024

Version #7

- Chronic obstructive pulmonary disease (requiring home oxygen)
- Renal failure
- Pregnancy
- Cognitive impairment
- Severe retinopathy or neuropathy.
- Other chronic disease or physical disability that would influence exercise intervention (e.g., recent spinal surgery)

No vulnerable populations will be targeted.

### 5.4 Recruitment Procedures

The research team will identify study candidates by manually examining the EPIC database for diabetes status and age or requesting a report from the Joint Data and Analytics Team (JDAT). Candidates will be reviewed to determine eligibility at the recommendation of their primary diabetes providers, who will be made aware of the study and eligibility criteria and introduce the study to the patients. The provider will be contacted to determine whether contact from the study team is appropriate. Eligible patients are contacted by the research team either via face-to-face meeting, phone, email, via video (Zoom), or approached at their regular clinic appointments to discuss their potential participation. Alternatively, the diabetes provider will send the patient a direct mailer or a MyChart message if they have a MyChart account (Appendix 13). These will only be sent once per patient.

The study will also be advertised so candidates may contact us proactively. Research flyers will be posted at the Yale Diabetes Center and public pharmacies. Internet postings, mass emails, and social media advertisements (e.g., Facebook, Google, Instagram) will also be used, particularly targeting T1D support groups such as BeyondType1.org. Leaders of private groups will be contacted and asked to consider posting advertisements. Study candidates identified on EPIC using the Joint Data and Analytics Team (JDAT) will receive a direct mailer, and those among them who have a MyChart account will receive a MyChart message. Lastly, the study will be posted on clinicaltrials.gov and our departmental website. Images and text for these advertisements are given in appendices 14 and 15 respectively. Full layouts are given in Appendix 15a.

Interested individuals viewing these advertisements will be invited to inquire about the study by a) contacting investigators by telephone or by email to learn more about the study, or b) providing their eligibility web questionnaire answers (Appendix 1b1) and contact details on a secure HIPAA-compliant Qualtrics webform (not capturing IP address or GPS location) so investigators may contact them by telephone or email. These individuals (i.e., inquirers) will be provided a brief description of the study and invited to ask questions. Among the inquirers, those wishing to volunteer will complete a brief eligibility interview (Appendix 1a, 1b, 1c). If they meet criteria, their primary care provider (PCP) will be contacted for confirmation (Appendix 24). If eligible, the participant will be invited to schedule a consenting televideo visit on Zoom, which they will be asked to complete from as private a physical setting as possible. They will be emailed a pdf of the consent form the same day as screening, to review in advance of the consenting visit. Consent will be documented by REDCap eConsent framework as detailed below.

### 5.5 Consent/Assent Procedures/HIPAA Authorization

- Consent/assent will use the standard IRB-approved compound consent / HIPAA research authorization form.
- A pdf of each IRB-approved form will be converted to an electronic survey on YCCI's approved REDCap e-consent framework. The framework adds to REDCap's typical survey framework by (a) a final screen displaying all responses as a pdf that participants are asked to certify, (b) storage of the form as a pdf rather than exportable data fields, and (c) fields allowing for "wet" signatures (hand-traced using the mousepad).
- The forms listed in the first bullet describe in detail the study intervention, study procedures, and risks. They are given to the participant and written electronic documentation of informed consent on these forms is required prior to starting study assessments and administering study intervention. Written electronic documentation on each form includes the signature of the researcher obtaining consent and the signature of the participant on the compound consent/authorization form.
- The participant will be asked to read and review the documents. The principal investigator, a co-investigator, or a research assistant will explain the research study to the participant (in terms suited to their comprehension) and answer any questions that may arise. This conversation will take place over a Zoom televideo call, which the participant will complete from as private a physical setting as possible.
- Participants will have the opportunity to carefully review the electronic written forms
  and ask questions prior to signing. To identify and clarify any misconceptions,
  participants will be encouraged to describe the research procedures and their
  associated risks in their own words, followed by correction of any errors by the
  researcher. A quiz is used to ensure understanding of study procedures. The
  participants will have the opportunity to discuss the study with their family or
  surrogates or think about it prior to agreeing to participate.
- Participants must be informed that participation is voluntary and that they may
  withdraw from the study at any time, without prejudice. A pdf of the signed
  consent/assent documents will be sent by encrypted email to the participants for their
  records.

This study does not involve children

# STUDY PROTOCOL Social Behavioral Template

# **6 Study Methods/Procedures**

6.1 Study Procedures

Table 1. Visit Schedule

	Pre-screening (Pre-consent)	Visit 1 Day 1	Visit 2 Day 8 ±7	Visit 3 Day 15 ±7	Visit 4 Day 22 ±7	Visits 5 Day 29 ±7	Visit 6 Day 36 ±7	Visit 7 Day 43 ±7	Visit 8 Day 50 ±7	Visit 9 Day 57 ±7	Visit 10 Day 64 ±7	Unscheduled Visit
Screening Phone Call	X											
Contact primary care provider for confirmation	X											
Informed Consent		X										
Demographics		X										
Clinical history		Χ										
Blood pressure			X	X	X	X	X	X	X	X	X	
Monitor symptoms		X	X	X	X	X	Х	X	X	X	X	
Devices			•				'				-	
InPen (if multiple daily injection user)			Continuou	ıs							>	
CGM			Continuo	ıs							>	
Fitbit			Continuo	ıs							>	
Morning survey monitoring daily living (Appendix 8a)			Continuou	ıs							>	
Actigraph GT9X (hip during day, wrist during night)			Continuou	IS	>				Continuous		>	
Intervention												
Mobile App					Continuou	s			>			
Outcome Evaluation											·	
Interview on App Features						X	X	X	X			
Exit Survey on App Features									X			

August 13, 2024 Version #7

Momentary Surveys on Motivation States									5x/day		>	
Weekly Survey on Motivation States			X	X	X	X	X	X	X	X	X	
Interview on Motivation States											X	
Adverse Events Reporting							-					
Adverse Events Reporting			X	X	X	X	X	X	X	X	X	X
Total Time (minutes)	15	30	45	35	65	65	65	65	85	35	80	15

\*The total time commitment for the study is the sum of these visits (575min) + mobile surveys (2min/survey \* 5 surveys/day \* 14 days = 140min) = 715 min, along with the target 150 minutes of exercise per week during the intervention and follow-up (150 min/week \* 6 weeks = 900min), for a total of 1625min or 27 hours.

[figure not shown]

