# STUDY PROTOCOL

# **Social Behavioral Template**

#### 6.1.1 Data Collection

#### STUDY DESIGN OVERVIEW

The study is a single-group longitudinal study with periods of familiarization with devices, intervention using devices and mobile app, and maintenance follow-up (Figure 4). The primary aim is observing the intervention for feasibility, acceptability, and mathematical robustness. The secondary aim is observing psychological and biometric outcomes through assessments (Table 2) which are completed 1x/weekly during the entire study to test long-term effects (hypothesis 2-1-2 & 2-2-1) and 5x/daily during maintenance follow-up to test momentary effects (hypothesis 2-1-1 & 2-2-2). The secondary aim also includes an interview at the end of the study (hypothesis 2-3).

**Figure 4.** Individual participant timeline. Blue indicates measures for primary aims and red indicates measures for secondary aims.

Table 2. Surveys used for secondary aims. Appendix has instruments for dependent variable (#2a,2b), independent

variables fear of hypoglycemia (#3a, 3b), exercise self	-efficacy (#4), exercise self-regulation (#	
valence (#6), daily intention and competing demands  PHASE	Momentary	Weekly
	(Hypotheses 2-1-1, 2-2-2) (Timepoints T1-T2)	(Hypotheses 2-1-2, 2-2-1) (Timepoints T0-T2)
ASSESSMENT SCHEDULE	5x daily at random times within 3hr bins under ambulatory conditions of daily living	Weekly in controlled setting (tele-video in quiet room)
DEPENDENT VARIABLE††		
Cravings for Rest and Volitional Energy Expenditure (CRAVE) survey of motivation states for physical activity*	Score of 1-item want "right now" and 1-item aversion "right now"	Score of 5-item want "past week" and 5-item aversion "past week"
INDEPENDENT VARIABLES		
Fear of hypoglycemia†	Score of 1-item "next 3 hours" version	Weekly score of 18-item "past week" version
Fear of hyperglycemia ††	Score of 1-item "next 3 hours" version	Weekly score of 24-item "past week" version
Blood glucose metrics‡	Past 3 hours averages and slope	Weekly averages
Exercise self-efficacy 	N/A	Weekly score of 9-item "past week" version
Exercise self-regulation 	N/A	Weekly score 15-item "past week" version
COVARIATES		
Non-T1D-related affective valence states previously associated with CRAVE score (pleasure/displeasure  , activation/arousal  ).§	Score of 1-item "right now" versions	Weekly score of 1-item "past week" versions
Day of week, time of day	Timestamp	N/A

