#### Mailing

After visit 1, participants will be mailed a package containing:

- a. Blood pressure monitor (Omron BP760N)
- b. CGM transmitter plus 6 sensors (Dexcom G6). If not already using. Issued by Dexcom under a research contract, not involving a prescription.
- c. Bluetooth ketone meter and test strips (Keto-Mojo GK+). The device also acts as a glucometer for CGM calibrations and sensor changes.
- d. Prepackaged snacks containing 15g fast-acting carbohydrates (e.g., Nestle Juicy Juice 125mL boxes, Glucose Tablets)
- e. Fitness smartwatch (Fitbit Inspire 3)
- f. Bluetooth Smart Insulin Pen (Companion Medical Inpen). If not a pump user. Issued by Medtronic under a research contract, not involving a prescription. A prescription for the participant's normal insulin in the correct cartridge for the InPen (3mL, U-100) will be obtained from the participant's primary diabetes care provider, or sent by a study physician through EPIC.
- g. Smartphone. If not already owned

August 13, 2024

Version #7

h. Actigraph GT9X Accelerometer. Programmed to run days 8-22, plus box to mail back so research team can download, reprogram for days 50-64, and mail to participant a second time.

In the event of lost items, up to 1 replacement will be provided, except items that are not essential for safety and have resale value (scale, fitness smartwatch, smartphone). Regardless of lost items, participants will be allowed to continue with other aspects of the study. For example, if they lose the smartwatch they can still use the exercise app with feedback missing the heart rate, steps, and sleep. Or if they lose the scale, they can still attend the weekly visits and complete the surveys and blood pressure readings. Participants will not be responsible for the cost of any lost or damaged items.

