#### **Start Ecological Momentary Assessments**

Ecological momentary assessments are repeated sampling of behaviors and experiences in real-time, which serves to a) minimize recall bias and b) capture the effect of real-world surroundings.

Participants will download Ilumivu or Qualtrics software. They will start momentary surveys 5x daily (Table 2, second column) and continue through the end of Visit 10. For each participant we will establish five windows programmed to cover their self-expected wake window. For example, a participant who normally wakes up at 7am and goes to bed at 10pm would have windows of 7-10am, 10am-1pm, 1pm-4pm, 4pm-7pm, 7pm-10pm. Ilumivu or Qualtrics will push one survey at a random time within each window. The survey remains accessible for 40min then expires if not completed. Participants will be instructed not to answer surveys while driving.

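### Table 1's ±7-day visit window conflicts with the fixed 2-4-2-week phases and with an accelerometer tied to study days 8-22 and 50-64; when used, it costs hypothesis 2-2-2 outcome data

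*Combined protocol and SAP*

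**What the plan says.** - **Windows.** Table 1 in Section 6.1 sets Visit 1 on Day 1 and Visits 2 to 10 on Days 8, 15, 22 and so on to 64, each ±7. The visits that matter most include "Visit 4 Day 22 ±7", "Visit 8 Day 50 ±7" and "Visit 10 Day 64 ±7".
- **Those visits bound the phases.** Devices, including the Actigraph, are set up at Visit 2. The app starts at Visit 4, and its row in Table 1 ends at Visit 8. At Visit 8, on the momentary surveys: "They will start momentary surveys 5x daily (Table 2, second column) and continue through the end of Visit 10".
- **Phase lengths are fixed elsewhere.** Section 4: "Single group completing familiarization (2 weeks), intervention (4 weeks) and follow-up (2 weeks". Section 4.1: "Subjects will each participate for 9 weeks". The time-commitment note under Table 1 counts 14 days of momentary surveys.
- **The accelerometer is tied to study days.** Section 6.1.1, Mailing, item h: "Programmed to run days 8-22, plus box to mail back so research team can download, reprogram for days 50-64". The Visit 8 procedures have the participant put the device back on at that visit.
- **What is not stated.** No text sets a minimum interval between visits, moves the Actigraph days with the visits, or says how a day is assigned to a phase in analysis.

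**The concern.** A window of ±7 days on visits 7 days apart does not constrain their spacing: neighbouring windows overlap. Because the same visits switch the app and the momentary surveys on and off, phase lengths move with them. The Actigraph runs, as written, do not.

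Three analyses depend on the alignment.

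- **Hypothesis 2-2-2** models the presence of an activity bout in a 3-hour window during follow-up. The Table 2 footnote makes Actigraph-measured activity the dependent variable for aim 2-2, so a survey day outside the recording has no outcome.
- **Hypothesis 2-2-1** compares activity across phases, so the baseline recording should contain only days before the app.
- **Hypotheses 2-1-2 and 2-2-1** use past-week scores. Two such surveys much less than 7 days apart cover overlapping days; much more than 7 days apart, they leave days uncovered.

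**Working it through.** **Inputs.** Nominal days and the ±7 window come from Table 1. The Actigraph days come from the Mailing list. Adherence, ICCs and variances come from Section 7.1. The window is read as counted from Day 1, which the table's format suggests but no text states.

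**1. The plan's own figures reproduce.** Familiarization 22 − 8 = 14 days; intervention 50 − 22 = 28; follow-up 64 − 50 = 14; total 64 − 1 = 63 days = 9 weeks.

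**2. What the window allows.** Visit 4 may fall on Days 15-29, Visit 8 on Days 43-57 and Visit 10 on Days 57-71.

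- Intervention: shortest 43 − 29 = 14 days; longest 57 − 15 = 42.
- Follow-up: longest 71 − 43 = 28 days. The arithmetic minimum, 57 − 57 = 0, would put Visits 8, 9 and 10 on one day. In order on distinct days, the minimum is 2 (for example Days 55, 56, 57).
- Familiarization: minimum 2 days on the same basis. The arithmetic maximum, 29 − 1 = 28, cannot be reached, because supplies are mailed after Visit 1 and so Visit 2 cannot be on Day 1.
- Adjacent visits: 1 to 21 days apart (7 + 14 = 21). At 1 day, two past-week surveys share 6 of 7 days; at 21 days, 21 − 7 = 14 days belong to neither.

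**3. Accelerometer coverage of follow-up.** Covered days = overlap of [Visit 8, Visit 10] with [50, 64].

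- Both visits 7 days late (Days 57 and 71): 64 − 57 = 7 of 14 days, or 7 × 5 = 35 of 70 prompts. Both 7 days early (Days 43 and 57): 57 − 50 = 7 of 14.
- Mean, dates uniform and continuous in the window (assumption). If both visits shift together by s, coverage is 14 − |s|, and the mean of |s| is 3.5, giving 10.5 days. If they shift independently, a late Visit 8 loses 1.75 days on average and an early Visit 10 another 1.75, again giving 10.5.
- Mean, normal scatter. The mean of |s| is 0.798 × SD. SD 2 gives 14 − 1.6 = 12.4 days; SD 3 gives 14 − 2.4 = 11.6.

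**4. Accelerometer coverage of baseline.** With Visit 2 on Day 15, the run that began on Day 8 loses 15 − 8 = 7 days, because the device has not yet been set up. With Visit 4 on Day 15, the stretch from Day 15 to Day 22 is recorded under the app: 7 of the run's 14 days.

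**5. Effect on hypothesis 2-1-1.** The expected 50 observations reproduce as 70 × 0.83 × 0.90 × 0.95 = 49.7. With m observations per person, design effect = 1 + (m − 1) × ICC, SE = √(variance × design effect / (21 × m)), and the effect is 0.34 × √variance. At one-sided 0.05, which comes closest to the stated 91%/81%:

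| Follow-up days | m | Power, want / aversion |
|---|---|---|
| 7 | 24.8 | 88% / 78% |
| 14 | 49.7 | 89% / 79% |
| 28 | 99.4 | 90% / 80% |

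The ICC dominates, so follow-up length matters little here.

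**The case against.** The strongest reply is that the intended schedule is clear. The 2-4-2-week design, the weekly assessments and the 14 survey days all say so. The payment total agrees: nine weekly payments rising from $5 by $3 ($153), 56 days × 3 items ($168), 28 days × 2 ($56) and $200 make $577. Section 9.4 counts any noncompliance as a deviation, so a 2-day follow-up would hardly pass as compliant. Visits are numbered with ordered content, so reversal is not a sensible reading. The second Actigraph run is programmed after the first is returned, and staff could set it to the real Visit 8. The affected hypotheses are secondary, and for 2-1-2, 2-2-1 and 2-2-2 only effect sizes are sought.

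Most of this stands. It makes the matter a contradiction to reconcile, not a design that truly runs for any length. It does not remove the problem: the ±7 in Table 1 and the fixed days in the Mailing list are the operating instructions, and following both loses data after an ordinary delay.

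A reader might also infer more than the documents support:

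- **That a late Visit 8 labels app days as maintenance in the second recording.** The device goes back on at Visit 8, so earlier recorded days are non-wear, which the plan screens by algorithm and participant logs. The loss is missing coverage, not mislabelled activity.
- **That many adjacent surveys would be bunched or out of order.** Any such percentage assumes that visits move independently. If a participant's visits shift together, the gaps stay at 7 days.
- **That glucose sensors run out.** Six sensors at 10 days cover 60 days against a nominal 64 − 8 = 56. A longer span is possible, but it is an edge case confined to participants issued study sensors.

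**Conclusion.** The concern holds as an inconsistency with a practical cost. Table 1, Section 4 and the Actigraph programming cannot all be met by a participant who uses the permitted window. The main cost falls on hypothesis 2-2-2: half the survey days lack an outcome if Visits 8 and 10 both slip by a week in the same direction, and on average 14 − 10.5 = 3.5 of 14 days (25%) are lost under uniform dates, or about 1.6-2.4 days with an SD of 2-3 days. A late Visit 2 shortens the baseline recording, and an early Visit 4 contaminates it with app days. Irregular spacing blurs the past-week scores.

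The averages rest on assumed date distributions, since the documents give none, and on the window being counted from Day 1. No material loss of power for hypothesis 2-1-1 should be claimed, and the primary feasibility and acceptability objectives are not put in doubt.

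**What to change.** 1. **Mailing, item h:** program each Actigraph run for 14 days from the booked Visit 2 and Visit 8 dates, replacing days 8-22 and 50-64. Book each visit before its device is sent.
2. **Table 1:** use a window narrower than half the spacing, such as ±3 days. Count Visits 3-4 from the actual Visit 2 date, Visits 5-8 from the actual Visit 4 date and Visits 9-10 from the actual Visit 8 date. All visits within a phase must share its anchor; re-anchoring only Visits 4, 8 and 10 could still put Visit 5 before Visit 4. Phases then run 14 ± 3, 28 ± 3 and 14 ± 3 days. Adjacent visits are 1-13 days apart and always in order.
3. **Section 7.2:** assign each day to a phase by actual visit dates.

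**Cost.** An amendment to the table, the mailing text and one analysis sentence, with no added visits. Somewhat more rescheduled visits will be logged as deviations. Two residuals remain: a 17-day follow-up would leave up to 3 survey days beyond a 14-day recording, and the Visit 2 to Visit 10 span could reach 17 + 31 + 17 = 65 days, so sensor supply should be checked against that.
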